### Table 1. Preliminary Operational Definitions of the Main Study Variables

CT24-WI-GL02-RF02 5.0 Non-Interventional Study Protocol Template For Secondary Data Collection Study 01-Aug-2023 Page 24 of 47

Variable	Definition for all countries unless otherwise specified	Role in the analysis
Cause-specific	As recorded in each database:	Safety event of
mortality (part of	The Danish Civil Registration System,	interest/endpoint
MACE)	The Danish Cause of Death Registry,	-
	The Swedish Cause of Death Register,	
	The French National Death Register (CepiDC)	

Table 1.	Preliminary O	perational Definitions	of the Main S	Study Variables
----------	---------------	------------------------	---------------	-----------------

\*Additional treatments may be defined in the SAP.

†Source of ICD-10 codes: France, inpatient hospital encounters; Denmark, Sweden, inpatient (hospital) or outpatient (specialist visits). ICD-10 codes with trailing letters are applicable in Denmark only.

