### Figure 1. Study Design Schema

```
Cohort accrual period [15 September 2023 – 14 September 2031]
(First dispensing of ritlecitinib, baricitinib or another approved systemic AA treatment)
Day 0 = index date in a given exposure cohort
```

Diagnosis of Alopecia areata [-5 years, 0 days]	
Exclusion: age <12 years on index date [0, 0]	
Exclusion: minimal residence [-365 days, -1 day]	
Washout period to define new users [-5 years, -1 day]	
	Follow up Window Days (1, Censor a ]

a. Earliest of: outcome of interest, or censoring by discontinuation/switch, death, disenrollment, end of the study period on 15 September 2033.

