### 9.3.4. Preliminary Operational Definitions of the Main Study Variables

Generally, in the participating data sources, disease is identified by diagnoses recorded at hospitalizations (all three countries) or at hospital-based specialist outpatient clinics (Denmark and Sweden). Diagnoses are currently coded using the World Health Organization (WHO) International Classification of Diseases, Tenth Revision (ICD-10). The Danish version of the ICD-10 may have more detailed codes compared with the WHO ICD-10. ICD-11 will be used if introduced during the study period. Treatment records originate, depending on the database, from outpatient dispensings, from hospital administrations, and are coded using the Anatomical Therapeutic Chemical (ATC) classification or local structured vocabularies (e.g., local treatment codes in Denmark).

Table 1 summarizes the initial operational definitions of the eligibility criteria, the exposure and the endpoints. The refined, country-specific definitions of all study variables as well as the final list of other variables with their operational definitions will be provided in the SAP.

Variable	Definition for all countries unless otherwise	Role in the analysis
	specified	
Age	In years	Eligibility criterion,
		demographic characteristic
Sex	Male, female, other	Demographic
		characteristic
Ritlecitinib	ATC code L04AF08	Exposure
Baricitinib*	ATC code L04AA37 (through 2023) L04AF02 (2024	Exposure
	onwards)	
	Treatment code BWHP106 (Denmark only)	
AA	ICD-10 code † L63	Eligibility criterion
Thromboembolic events	ICD-10 codes † I26, I260A I269A, I67.6, I74, I80.1,	Safety event of
(including DVT, PE,	180.2, 181, 182.0, 182.2; 182.3, 182.8, 182.9 022.3,	interest/endpoint
and arterial thrombosis)	087.0, 087.1, 0882D, 0882E, T817D	
HZ	ICD-10 codes † B01, B02, H031F, H131M, G051M,	Safety event of
	H190D, H192D, H190J, H220C, B027, B028, B029,	interest/endpoint
	G0511, H621B	
	ATC codes J05AB01 (HZ-specific tablet dose 800 mg	
	in package of 35 tablets based on product code)	
	J05AB11 (HZ-specific tablet dose: 500 mg based on	
	product code)	
	J05AB09 (HZ-specific tablet dose: 500 mg based on	
	product code) (23)	
Serious infection	ICD-10 codes† as the primary diagnosis at a hospital	Safety event of
	contact with a minimum of 1 overnight stay (24) A00-	interest/endpoint
	B99, D/3.3, E06.0, E32.1, G00-G02, G04.2, G05-G07,	
	H00.0, H44.0, H60.0-H60.3, H66-H67, H70, I30.1,	

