NMSC	France: treatment proxy if relevant	
	Only incident primary malignancies will be considered	
NMSC	ICD-10 codes† C44	Safety event of
		interest/endpoint

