
### 9.4.3. Sweden

Similar to Denmark, the Swedish register system is a large, complete source of populationbased data from the entire Swedish population (10.64 million in 2023). Data from the Swedish Total Population Register and the Swedish National Health Registers, including the Swedish National Patient Register, Prescribed Drug Register, Total Population Register, Swedish Cause of Death Register, and Swedish Cancer Register will be used. A unique personal identification number is issued to all residents of Sweden upon birth or immigration and is used unchanged throughout life. The personal identification number is used to link patient-level data across the various registers. All citizens, independent of socioeconomic status, have unrestricted access to health services including partial or complete

PFIZER CONFIDENTIAL

CT24-WI-GL02-RF02 5.0 Non-Interventional Study Protocol Template For Secondary Data Collection Study 01-Aug-2023

reimbursement of purchased medicines due to the tax-supported public health service with universal coverage. The Swedish National Patient Register includes diagnosis information for inpatients at public hospitals and outpatient specialists' visits, including primary and secondary diagnoses and surgical procedures. The Prescribed Drug Register includes information on all prescribed drugs dispensed in outpatient settings in Sweden since 01 July 2005. The register contains patient level data on dispensed medicines for the entire Swedish population, including information on the dispensed drug as well as the dates of prescription and dispensing (20, 46-49). The coding systems for diagnoses, procedures, and medications are similar in Denmark and Sweden.

All three research centres and associated data sources are listed in the European Network of Centres for Pharmacoepidemiology and Pharmacovigilance (ENCePP) Register.

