# 9.7.2. Analyses of the Primary Objectives

The primary analysis will comprise estimation of IRs with 95% CIs for the safety events of interest using a time-to-event analysis (except the growth metrics, which will be reported using means, medians or percentiles as appropriate). The analyses will include:

- Total number of patients in each exposure cohort
- Number of each new safety event of interest observed during the follow-up time in each exposure cohort
- Crude IRs (and cumulative incidences over selected prespecified periods) of the safety events of interest and 95% CIs in each exposure cohort
- Age- and sex-standardized IRs and 95% CIs in each exposure cohort

The summary of event rates will report time to first event since index date for each exposure cohort with appropriate censoring rules applied for those who do not experience an event by the end of the follow-up period, including those who die and those who emigrate. Rates will be expressed as events/10,000 person-years (PYs) of follow-up or a larger denominator if appropriate.

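### Underlying cause of death counts only towards MACE, so the thromboembolic and infection rates miss fatal events that never produced a qualifying hospital record

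*Protocol*

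**What the plan says.** Table 1 in section 9.3.4 lists ICD-10 codes for each endpoint. A dagger marks the codes for thromboembolic events, serious infection and opportunistic infection, and its footnote names where they are read: "Source of ICD-10 codes: France, inpatient hospital encounters; Denmark, Sweden, inpatient (hospital) or outpatient (specialist visits". Death certificates are not among those sources. Serious infection must also be the primary diagnosis at a hospital "contact with a minimum of 1 overnight stay".

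Underlying cause of death appears in one endpoint definition only. The MACE row accepts any code from I00 to I99 on the death certificate, and the separate row for cause-specific mortality is labelled as part of MACE.

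A death that is not an event ends follow-up. Figure 1 lists "censoring by discontinuation/switch, death, disenrollment" among the reasons for ending it, and section 9.7.2 applies censoring "for those who do not experience an event by the end of the follow-up period, including those who die and those who emigrate".

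Section 9.9 admits in general terms that outcomes are measured as hospitalisation or treatment-proxy rates. It discusses incomplete cause-of-death data for MACE only.

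**The concern.** The primary objective is the absolute incidence rate of each safety event. Death before hospital care, or within hours of arrival, is the most severe form of pulmonary embolism or infection, and it is the form that these definitions can miss. An overnight-stay rule intended to select serious infections also removes patients who die too early to meet it.

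The effect runs in one direction: the numerator loses events while the person-time stays the same. Because absolute rates are the primary result, similar under-capture in the baricitinib cohort would not correct the ritlecitinib rate. Section 9.2 relies on most events needing immediate hospital or specialist treatment, which does not cover patients who die before receiving it.

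**Working it through.** **Inputs**
- Ritlecitinib accrual by year (Table 2) and years of follow-up (section 9.5).
- Background rates per 1,000 person-years (Table 3): thromboembolic events 1.17, serious infections 1.89. No rate is given for opportunistic infections.
- Code sources, overnight rule and MACE death codes (Table 1); censoring rules (Figure 1, section 9.7.2).

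**Step 1: the plan's own figures.** 0×9 + 74×8 + 96×7 + 110×6 + 127×5 + 144×4 + 161×3 + 123×2 = 3,864 person-years, as stated. At 1:1 the total is 7,728. Expected events are 7,728 × 1.17/1,000 = 9.04 and 7,728 × 1.89/1,000 = 14.61. The protocol gives 10 and 15, so it rounds up.

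**Step 2: ritlecitinib cohort alone.** Thromboembolic events: 3,864 × 1.17/1,000 = 4.52. Serious infections: 3,864 × 1.89/1,000 = 7.30.

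**Step 3: deaths traced through the definitions**
- *Pulmonary embolism outside hospital, known only from the death certificate (I26).* I26 is on the thromboembolic list, but the footnote does not admit death certificates, so there is no thromboembolic event. I26 lies within I00-I99, so MACE counts it.
- *Infection outside hospital, known only from the death certificate.* Neither a serious nor an opportunistic infection is recorded. Almost all the listed infection codes lie outside I00-I99 (I30.1 and I40.0 are exceptions), so MACE does not pick it up either.
- *Infection, with death on the day of admission.* The overnight rule fails, so no serious infection is recorded. An opportunistic infection can still count if a listed code is recorded, because that row has no overnight rule.
- *Either cause, with death after at least one night and a qualifying code.* This is captured. The gap does not extend to deaths in hospital generally.

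**Step 4: what one missed event means.** If one further event is missed beyond the expected number, the rate is understated by 1/(4.52 + 1) = 18% for thromboembolic events and by 1/(7.30 + 1) = 12% for serious infections.

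**Step 5: illustration under an assumed share.** The documents do not say what share f of first events is seen only at death. Assume f between 5% and 30%. The rate is then understated by the fraction f.
- If the Table 3 rates contain hospital-recorded events only, missed events are E × f/(1 − f). Thromboembolic: 4.52 × 0.05/0.95 = 0.24 to 4.52 × 0.30/0.70 = 1.94. Serious infection: 7.30 × 0.05/0.95 = 0.38 to 7.30 × 0.30/0.70 = 3.13.
- If the Table 3 rates already include such deaths, missed events are E × f. Thromboembolic: 4.52 × 0.05 = 0.23 to 4.52 × 0.30 = 1.36. Serious infection: 7.30 × 0.05 = 0.37 to 7.30 × 0.30 = 2.19.

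**The case against.** The strongest reply is that Table 1 is preliminary. The SAP is to refine the definitions, and the cause-of-death registers of all three countries are already listed, so nothing prevents the SAP from using them more widely. That is true, but the protocol is not merely silent: the footnote names the sources, and the mortality row assigns cause of death to MACE. Section 9.7 also says that a major change to a primary endpoint definition goes into a protocol amendment.

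Second, person-time ends at death in any case, so censoring at death is normal for an incidence rate. This stands. The defect is in counting events, not in the censoring.

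Third, random error is larger: with 4 events observed, exact 95% Poisson limits are about 1.1 to 10.2. This also stands, but a confidence interval does not reflect events that the definition cannot record.

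Fourth, the overnight rule follows a cited source. That supports keeping it for the main rate, not leaving its effect on early deaths unexamined.

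Two stronger readings are tempting, and the documents do not support them.
- *A reader might extend the point to malignancy.* Section 9.4.3 says of further Swedish sources: "Swedish Cause of Death Register, and Swedish Cancer Register will be used". Table 1 adds "France: treatment proxy if relevant". A hospital code is therefore not the only route. Dating a cancer at death would also sit badly with the restriction to incident primary cancers and with the induction period.
- *A reader might call it a contradiction that one death counts for MACE and not for thromboembolism.* These are two separately defined endpoints, and different results follow from different definitions.

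**Conclusion.** The point holds for thromboembolic events, serious infections and opportunistic infections. As Table 1 is written, their rates are biased low because fatal events without a qualifying hospital or specialist record are not counted. The direction follows from the text. The size does not: the ranges in step 5 rest on an assumed share of 5-30% and must not be read as estimates.

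The point matters because expected ritlecitinib counts are small (about 4.5 and 7.3). They are also on the high side for an on-treatment analysis, since 3,864 person-years assumes no loss to follow-up and makes no allowance for censoring at discontinuation. Results are reported by country, which divides the counts further. That a fatal pulmonary embolism still reaches MACE is only partial comfort. Fatal infections mostly do not, and the MACE row also permits a fallback based on death within 30 days of a diagnosis, which would not capture a death with no prior diagnosis.

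**What to change.** Keep the hospital-based rates as defined. Alongside them, for thromboembolic events, serious infections and opportunistic infections, report a version that:
- counts as an event, on the date of death, an underlying cause of death within the codes already listed for that endpoint;
- does not require the overnight stay for serious infection when the patient dies during the contact;
- applies the same exclusion of prevalent conditions as the main analysis;
- stops at the last date with complete cause-of-death data in each country, with that date stated.

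Add this to the relevant rows and the footnote of Table 1 and to section 9.7.2, and name the limitation in section 9.9. Leave malignancy out.

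The cost is modest programming on registers already listed. One drawback is that causes of death are coded less specifically than hospital diagnoses, which is why both versions should be shown. The other is the 2-3 year lag. Counting back from September 2035, data would be complete to about September 2033 (nothing lost) or September 2032. In the latter case the final year of all 835 patients is lost, leaving 3,864 − 835 = 3,029 person-years on the protocol's assumptions. Interim reports would be truncated as well.

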### 9.4. Data Sources

This study will utilize routinely collected data from population-based registers in Denmark and Sweden, and an administrative healthcare database in France.

### 9.4.1. Denmark

Denmark's population-based registers, linkable by a unique identifier, the central person registration (CPR) number, assigned by the CPR registry to all residents at birth or upon immigration contain routinely collected data for the country's entire population of more than 5.8 million individuals and allow long-term follow-up of individuals for assessment of safety events such as MACE or malignancy (27, 28). The CPR registry contains information on age, sex, migrations and deaths. The Danish National Prescription Registry contains information on all prescription medicines dispensed at Danish community pharmacies with products recorded via ATC codes. Indication may be recorded for certain dispensings (21). Certain drugs administered at specialist hospital-based clinics are captured in the Danish National Patient Register, and tentatively from 2024, in the Danish Hospital Medicines Register (currently in development and expected to become complete in 2024 (29)). Newly approved drugs, especially expensive treatments, are often first prescribed or administered at the specialist hospital clinics with follow-up with general practitioners. Such treatments (active substance) may be identifiable via procedure/treatment codes in the Danish National Patient Registry. The Danish National Patient Registry records diagnoses (using a Danish version of the WHO ICD-10/ICD-11 codes) and procedures (using the Nordic Medical Statistical Committee NOMESCO codes) during inpatient or outpatient hospital encounters. The Danish Cause of Death Registry records causes of death using ICD-10 code categories. The Danish National Health Services Register may be used to identify procedures and specialist referrals associated with hearing loss. The Danish Children's Database captures height and weight from routine school examinations and contains data until children reach age 16 years. Most of these databases have been used extensively for pharmacovigilance, and multiple algorithms have been validated (23, 30-37).

### 9.4.2. France

The French nationwide administrative database (Système National des Données de Santé – SNDS; French Administrative Healthcare Database) covers more than 99% of the French population – near 67 million inhabitants – from birth (or immigration) to death (or

PFIZER CONFIDENTIAL

CT24-WI-GL02-RF02 5.0 Non-Interventional Study Protocol Template For Secondary Data Collection Study 01-Aug-2023 Page 25 of 47

emigration), even if a subject moves, changes occupation or retires (38, 39). Using a unique pseudonymized identifier, it merges all reimbursed outpatient claims from all French healthcare insurance schemes with hospital-discharge summaries from public and private hospitals, and the national death registry. Thus, all reimbursed medical and paramedical encounters are recorded. SNDS captures general characteristics (e.g., gender, year of birth, affiliation scheme, area of residence); registration for Long Term Disease with the diagnosis code, qualifying for full health insurance coverage; outpatient encounter details (e.g., medical and paramedical visits with practitioner specialty, medical and imaging procedures, laboratory tests, quantity of drugs dispensed, drug strength, medical devices; but no indication, physician prescription directions, drug posology or exam results); inpatient details (e.g., primary and associated hospital discharge diagnoses, procedures and laboratory tests performed, innovative or expensive drugs and medical devices invoiced in addition to the hospitalization, length of the hospital stay). Dates, associated costs, and prescriber and caregiver information are provided for each expenditure. Diagnoses are coded using the WHO ICD-10 codes. Drug dispensings are identified and captured through ATC codes, but also at the package level in outpatient settings with the Code Identifiant de Présentation (CIP; Presentation Identification Code), and at the unit of administration level in inpatient settings through the Unité Commune de Dispensation (UCD; Common Dispensing Unit). Procedures are coded according to the Classification Commune des Actes Médicaux (CCAM; Common Classification of Medical Procedures), and laboratory tests follow the Nomenclature des Actes de Biologie Médicale (NABM; Nomenclature of Medical Biology Acts). The SNDS database also includes The French National Death Register (CepiDC) data. Though neither medical indication nor result are recorded, the level of detail of the captured information enables an accurate characterization of patient healthcare journeys (40). SNDS has been used in multiple completed and ongoing studies that include endpoints (VTE (41), infections (42), CVD algorithms (43), malignancies (44)) and other variable definitions relevant for the current study (JAK inhibitors (45)). Access to these data sources is strictly regulated by French law and needs approval from the Committee in Health data research (Comité Ethique et Scientifique pour les Recherches, les Etudes et les Evaluations dans le domaine de la Santé - CESREES), and from the French data protection commission (Commission Nationale de l'Informatique et des Libertés – CNIL). Four to six months are required to obtain CESREES and CNIL approvals. An agreement between the CNAM and the SNDS research partner then needs to be signed to access data extraction. BPE will oversee requesting access to SNDS data.

### 9.4.3. Sweden

Similar to Denmark, the Swedish register system is a large, complete source of populationbased data from the entire Swedish population (10.64 million in 2023). Data from the Swedish Total Population Register and the Swedish National Health Registers, including the Swedish National Patient Register, Prescribed Drug Register, Total Population Register, Swedish Cause of Death Register, and Swedish Cancer Register will be used. A unique personal identification number is issued to all residents of Sweden upon birth or immigration and is used unchanged throughout life. The personal identification number is used to link patient-level data across the various registers. All citizens, independent of socioeconomic status, have unrestricted access to health services including partial or complete

PFIZER CONFIDENTIAL

CT24-WI-GL02-RF02 5.0 Non-Interventional Study Protocol Template For Secondary Data Collection Study 01-Aug-2023

reimbursement of purchased medicines due to the tax-supported public health service with universal coverage. The Swedish National Patient Register includes diagnosis information for inpatients at public hospitals and outpatient specialists' visits, including primary and secondary diagnoses and surgical procedures. The Prescribed Drug Register includes information on all prescribed drugs dispensed in outpatient settings in Sweden since 01 July 2005. The register contains patient level data on dispensed medicines for the entire Swedish population, including information on the dispensed drug as well as the dates of prescription and dispensing (20, 46-49). The coding systems for diagnoses, procedures, and medications are similar in Denmark and Sweden.

All three research centres and associated data sources are listed in the European Network of Centres for Pharmacoepidemiology and Pharmacovigilance (ENCePP) Register.

### 9.5. Study Size

All ritlecitinib-treated patients meeting study inclusion and exclusion criteria in all data sources during the accrual period will be included in the study. Estimated anticipated group size of the ritlecitinib-exposed population across the three databases is provided in Table 2. Overall, an estimated 835 ritlecitinib-exposed patients are expected to be accrued over 8 years. Of note, these sample size calculations are estimates based on the projected uptake of ritlecitinib in the study countries and are subject to the actual uptake and final study inclusion and exclusion criteria.

			Y	ears Post-	-Approval			
	Year 1	Year 2	Year 3	Year 4	Year 5	Year 6	Year 7	Year 8
Estimated New Patients Treated Per Year in Denmark, France, and Sweden (based on projected market uptake)	0	148	192	220	255	288	321	247
Estimated 50% Meeting Eligibility Criteria (conservative estimate, true proportion may be higher)	0	74	96	110	127	144	161	123
Estimated Cumulative Number of Patients Exposed to Ritlecitinib	0	74	170	280	407	551	712	835

